### **1.3 Schedule of Activities (SoA)**

Visit procedures must be completed on a single day, except screening period.

Please note that if screening parameters are available as part of routine medical practice, these are not required to be repeated as long as they were measured within 14 days of screening and meet the thresholds defined in the in-/exclusion criteria.

It is not allowed to perform dialyses which are linked to study visits outside of the study center. Participants should come to the same dialysis center for each visit. Visits in between dialyses, i.e. not linked to a study visit, can be performed outside of the study center.

PD and biomarker sampling and analyses are mandatory for all participants except China and have to be done according to the SoA.

Please refer to [Table 1–1](#) for the Schedule of Activities of the main treatment period and to [Table 1–2](#) for the Schedule of Activities of the extension treatment period and the follow-up period.

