**Table 1–1: Schedule of Activities: Main Treatment Period**

Study period (Duration)	Pre-treatment period (7 days)			Main treatment period d (6 months)																Notes			
	Visit number	1	2	3	4	5	6	7	8	9	10	11	12	13	14	15	16	17	18		EOMT b ED a		
Study intervention LD or MD	SCR c	RND			LD			MD			MD		MD		MD		MD						
Approx. month	Day				Day since last study intervention dose																		
	-13 to 1	1	3	6	8	2	4	30	2	4	30	4	30	4	30	4	30	4	30	4		30	
Approx. month	-	1	1	1	1	1	1	2	2	2	3	3	4	4	5	5	6	6	7				
Window (days)			+3	+3	+3	+3	+3	+3	+3	+3	±3	+3	±3	+3	±3	+3	±3	+3	±3	+3	±3	A deviation of 2-3 days equals 1 dialysis session. Section 7.1.	
Central laboratory	Biomarker genetics e (if applicable)				•																	Pre-dialysis. Prior to study intervention.	
	Biomarker e : FVIII, FIX, FXII, vWF antigen, vWF activity				•																		
	Biomarkers e				•						•									•	•		
	Main PD e samples				•	•	•	•	•	•										•	•		•
	Additional PD e samples				•																		•
	PK samples				•	•	•	•	•	•	•									•	•		•
ADA/NAB				•	•	•	•	•	•	•									•	•	•		

Abbreviations: ADA = anti-drug antibodies, AE = adverse event, AESI = adverse event of special interest, Approx. = approximately, AV = arteriovenous, BUN = blood urea nitrogen, ECG = electrocardiogram, ED = early discontinuation visit, EOET = end of extension treatment period visit, EOMT = end of main treatment period visit, IWRS = interactive web response system, Kt/V – K = dialyzer urea clearance, t = dialysis time, V = total volume of distribution of urea, LD = loading dose, MD = maintenance/ monthly dose, NAB = neutralizing antibodies, PD = pharmacodynamic, PK = pharmacokinetic, RND = randomization, SAE = serious adverse event, sc = subcutaneous, SCR = screening, SQCS = semi-quantitative clotting score, URR = urea reduction ratio

- a. It is recommended to perform the ED visit approximately 1 month after last study intervention. After ED the participant moves directly to the follow-up period.
- b. EOMT and visit 19 will be performed at the same day. Both of them are mandatory separate visits and shouldn't be missed.

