- Pre-treatment period (from visit 2 until visit 4): 7 days
- Main treatment period (from visit 5 until EOMT visit): 6 months
- Extension treatment period (from visit 19 until EOET visit): up to 12 months
- Follow-up period (from visit 32 until visit 35): 4 months after end of treatment (EOMT or EOET)

Informed consent form will be obtained at the beginning of the screening period. During the screening period, subject's eligibility evaluations will be performed. Subjects will be randomized either to osocimab or to placebo using a covariate-adaptive randomization technique (minimization methods) (for details see Section 6.3).

During the pre-treatment period, which will serve as a baseline period, a series of 3 hemodialysis sessions will be performed. Unfractionated or low molecular weight heparin (UFH/LMWH) is allowed as anticoagulation for maintenance of hemodialysis treatment during the whole study duration.

The study intervention will be administered subcutaneously abdominal with one single loading dose at visit 5 and monthly maintenance doses from visit 8 onwards until the end of the extension treatment period with an overall maximum of 18 months of treatment. The main treatment period consists of 6 months of treatment as this time frame is deemed to be the minimum clinically relevant treatment time to assess osocimab as chronic life-time treatment in an appropriate manner and in preparation for Phase 3.

Study intervention will be administered during the extension treatment period for up to a maximum of 12 months or until the last subject randomized to the study has performed the EOMT visit (whichever comes first).

The treatment period (main or extension) will end with the study assessments performed 30 days after the last study intervention administration.

The follow-up period is an observational period of 4 months, i.e. ends approximately 5 months after the administration of the last dose of osocimab.

[figure not shown]
All suspected bleeding and cardiovascular (CV) or thromboembolic (TE) events occurring after signing informed consent (randomized subjects only) will be adjudicated by the CIAC in a blinded fashion; blinded to treatment allocation and dose cohort (details are described in the CIAC charter).

The procedures followed by the CIAC are detailed in the CIAC charter. Detailed instructions regarding documentation, reporting and transfer of adjudication dossiers will be provided in a study specific guidance document.

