4.3 Handling of Missing Data

All missing or partial data will be presented in the subject data listing as they are recorded on the Case Report Form (CRF).

General rules

When appropriate, the following rules will be implemented so as not to exclude subjects from statistical analyses due to missing or incomplete data:

- **Efficacy and Safety clinical variables, adverse events**
For cases where start month and year are reported but day is missing, impute the maximum of (date of randomization + 1 week, first date of study intervention, 01.month.year). For cases where only start year is reported, impute the maximum of (date of randomization + 1 week, first date of study intervention, 01.01.year), but not later than death date if the patient died.
- **PD variables**
No imputation will be done for pharmacodynamic parameters.
- **Study intervention start date**
If the start date and time is missing it will be imputed with the randomization date + 1

week and time. If start date and time is recorded as earlier than randomization and cannot be clarified, date and time of randomization will be used for the statistical analysis.

- **Study intervention stop date**

If the stop day is missing, but the stop month and stop year are available then the stop date will be imputed as minimum of (15.month.year and last study visit date in main treatment or extension treatment period and death date).

If the stop day and month are missing then the stop date will be imputed as minimum of (the last study visit date before the post treatment follow-up period and death date).

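### Two fallback rules in SAP 4.3 misdate injections when triggered: the last dose falls about 30 days late if stop day and month are missing, and the first dose at least 7 days early if recorded before randomisation

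*SAP*

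**What the plan says.** SAP 4.3 (Handling of Missing Data) has four rules for study-drug dates:

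- Start missing: "If the start date and time is missing it will be imputed with the randomization date + 1" week.
- Start recorded too early: "If start date and time is recorded as earlier than randomization and cannot be clarified, date and time of randomization will be used".
- Stop day missing, month and year known: the date is "imputed as minimum of (15.month.year and last study visit date in main treatment or extension treatment period and death date", closing bracket omitted.
- Stop day and month missing: the date is the "minimum of (the last study visit date before the post treatment follow-up period and death date", closing bracket omitted.

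The schedule is fixed elsewhere. SAP 3 lists "Pre-treatment period (from visit 2 until visit 4): 7 days", and Protocol Table 1–1 puts the first injection at visit 5, day 8. SAP 3 also states: "The treatment period (main or extension) will end with the study assessments performed 30 days after the last study intervention administration". For early discontinuation (ED), footnote a of Protocol Table 1–1 says "It is recommended to perform the ED visit approximately 1 month after last study intervention". Protocol 1.2 agrees: follow-up ends 5 months after the last dose and 4 months after EOMT or EOET.

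SAP 4.5 calls an event treatment emergent from the start of treatment to 30 days after the last administration. SAP 6.4.1 treats last administration plus 30 days as a competing event when treatment ends prematurely. It counts only events that begin after the first dose and within the main treatment period, and it censors at EOMT or when data collection stops.

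**The concern.** Two of the four rules would suit a daily drug started at randomisation and taken until the final visit. Here every dose is a dated injection at a known visit. The final treatment-period visit is normally a check one month after the last dose, and a week of pre-treatment separates randomisation from the first dose.

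First and last administration dates set time zero, the treatment-emergent flag, the timing of the competing event and the person-time denominator for both primary endpoints. A last dose placed too late lets off-treatment events count as primary events and lengthens exposure. Those extra days would hold data, because participants who stop the drug stay in the study (SAP 4.2) and adverse events are collected to the last follow-up visit (Protocol 8.3.1). A first dose placed too early turns pre-dose events into treatment-emergent ones, against SAP 6.4.1 and Protocol 9.4.2, which both exclude them.

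**Working it through.** **Plan's own figure.** In Protocol Table 1–1 the main-period doses fall at visits 5, 8, 11, 13, 15 and 17. At 30-day spacing these are days 0, 30, 60, 90, 120 and 150 from first dose. EOMT = 150 + 30 = day 180 = 6 × 30 days, which reproduces the stated 6 months. The 30-day gap is confirmed by 5 − 4 = 1 month in Protocol 1.2.

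**Stop day and month missing.** Assume the final visit is EOMT or an ED visit 30 days after the last dose.

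- True end of exposure = last dose + 30.
- Imputed end = (last dose + 30) + 30, cut at EOMT (day 180).

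| True last dose (day) | Final visit | True end | Imputed end, capped | Excess days |
|---|---|---|---|---|
| 0 | 30 | 30 | 60 | 30 |
| 30 | 60 | 60 | 90 | 30 |
| 60 | 90 | 90 | 120 | 30 |
| 90 | 120 | 120 | 150 | 30 |
| 120 | 150 | 150 | 180 | 30 |
| 150 (main-period completer) | 180 | 180 | 180 | 0 |

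With the ±3-day visit window the final visit is 27 to 33 days after the dose, so the uncapped window closes 57 to 63 days after it. A participant whose last dose is in the extension has 0 excess days in the primary analysis. If a participant is lost without an ED visit, the last visit may itself be a dosing visit (0 days late) or a visit 2 to 4 days after a dose.

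The overall-period analysis (SAP 6.4.2) is exposed for those who stop early in either period; anyone who reaches EOET is protected by censoring there. The 5-month full-study window in SAP 4.5 moves by the same 30 days, although scheduled visits end about 150 days after the true last dose.

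**Start recorded before randomisation.** Randomisation is day 1 and the first dose day 8, with a +3-day window.

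- Pre-randomisation rule: 8 − 1 = 7 days early, up to 11 − 1 = 10.
- Missing-start rule: 8 − (1 + 7) = 0 days early, up to 11 − 8 = 3.

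**Size for bleeding.** The rate is 10 per 100 participant-years (Protocol 9.2, placebo). I assume a constant hazard and a participant still event-free. Added risk = 1 − exp(−rate × days / 365.25).

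- 30 days: 1 − exp(−0.10 × 30 / 365.25) = 0.0082, about 0.8 percentage points.
- 7 days: 1 − exp(−0.10 × 7 / 365.25) = 0.0019, about 0.2 percentage points.

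The documents do not allow the number of affected participants to be calculated.

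**The case against.** The strongest reply is that these rules will hardly ever operate. Site staff give every injection, the date and time go into source and eCRF, and the vial number is confirmed at dosing (Protocol 6.4). The pre-randomisation rule applies only after clarification has failed. This stands, and it keeps the point small.

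The second reply is that the longer window may not reach the primary analysis even for early discontinuers. After the ED visit a participant passes into follow-up, SAP 6.4.1 counts only main-period events, and Protocol 9.4.2 censors at the last main-period data if that comes first. On that reading the excess disappears. But SAP 4.5 refers to the scheduled main treatment period, and SAP 6.4.1 names EOMT and the end of data collection, not the ED visit, as censoring points. The ambiguity is real and unresolved.

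A reader might also infer more than the documents support:

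- **That a missing start date is placed at randomisation.** It is placed one week later, which matches day 8. Only the recorded-before-randomisation case is wrong.
- **That all incomplete stop dates are about 30 days late.** With only the day missing, the 15th is a roughly centred convention: over true days 1 to 30 the error runs from −15 to +14 days, with mean 15 − 15.5 = −0.5. Death also caps both stop rules.
- **That the adverse-event composite is badly distorted.** No rate for it is given. At an assumed 100 to 200 per 100 participant-years, 30 days carry 7.9% to 15.1% risk among those still event-free. Many will already have had a first event. Multiplying by the proportion event-free at the true end of exposure gives 7.3% to 12.9% after a last dose on day 0 and 5.2% to 6.7% after one on day 120. These are illustrations per affected participant, not estimates for the trial.

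**Conclusion.** The point holds in a limited form and is minor. Both are stated rules that give a wrong date when triggered, not merely missing detail.

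- The stop rule is about 30 days late when day and month are both missing and the last visit is EOMT, EOET or an ED visit at about one month. In the primary analysis this can affect only early discontinuers in the main period, subject to the ambiguity above.
- The start rule for dates recorded before randomisation is at least 7 days early and contradicts the rule beside it.

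For bleeding the cost is about 0.8 percentage points per participant with 30 excess days and about 0.2 for 7 days. With few participants affected, the effect on the hazard ratio should be minor. This assumes that the start and stop dates in SAP 4.3 are the first and last administration dates used in SAP 4.5 and 6.4.1, that visits follow the schedule, and that the planning rate applies to the extra days.

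**What to change.** Replace the dose-date rules in SAP 4.3 with one principle. A missing, partial or impossible injection date takes the date of the dosing visit at which that injection was recorded, capped at death:

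- First dose: the visit 5 date. If that is unusable, randomisation + 7 days.
- Last dose: the last visit with a recorded administration or vial number.
- EOMT date: use it as a dose date only when visit 19 dosing is recorded that day. The two visits share a day and visit 19 is a dosing visit, so a blanket ban would exclude the true date for someone last dosed there.
- EOET and ED dates: do not use them as dose dates.

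The visit date is a sound substitute because Protocol 1.3 requires that "Visit procedures must be completed on a single day, except screening period". SAP 6.4.1 should also say whether the main treatment period of an early discontinuer ends at the ED visit. The cost is a few lines of SAP text and derivation code, using visit and vial records already collected. A listing of participants with an imputed dose date would show whether the rules were ever used.

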4.4 Interim Analyses and Data Monitoring

No formal interim analysis is planned.

The primary analysis will be performed after all subjects have completed the main treatment period (primary completion).

A full analysis will be performed after the last subject has completed the follow-up of 4 months (study completion). Of note, the full analysis, or better the evaluation of the data collected after the main treatment period will be considered open-label due to the unblinding caused by the primary analysis.

Furthermore, the DMC will frequently review safety data to ensure the safety of the subjects in the ongoing study. The required tables and listings will be created by an independent Statistical Analysis Center (SAC). Only the open session of the DMC meetings may be attended by representatives of the Sponsor. Overall treatment data presented here may include enrollment data, adverse event data, baseline characteristics, update on study status or any potential issues, outcome data. More details can be found in the Data Monitoring Committee Charter.

4.5 Data Rules

The pre-treatment period serves as baseline period and takes place before first study intervention was given. If there is more than one measurement, the mean of the respective measures will serve as baseline.

Baseline for PD will be visit 5 data prior to dosing.

The primary analysis will be based on all respective events that occurred during the scheduled main treatment period.

Additional analyses may be based on all respective events that occurred during the overall study period, consisting of both the main treatment and extension treatment period.

In addition, further analyses may be based on all events occurring during the full study period consisting of the main treatment, extension treatment and post-treatment follow-up period.

These time scopes are summarized in the table below.

An event is considered treatment emergent if it occurred between start of treatment and not later than 30 days after last administration of study intervention.

An event is considered as full study treatment emergent if it occurred between first study intervention and not later than 5 months after last administration of study intervention.

Additional analysis may be performed post-hoc.

Time scope definition:

Overall study period	Main treatment phase + extension treatment phase
Full study period	Main treatment phase, extension treatment phase + follow up

4.5.1 Laboratory measurements

Numeric laboratory measurements outside the calibration range, marked by “<x” (<LLOQ) or “>x” (>ULOQ) will be replaced by LLOQ/2 or ULOQ, respectively, in the statistical analysis.

For the analysis of PD, means and standard deviation will only be calculated if at least 2/3 of the individual data were measured and were within the calibration range.

Laboratory records without a RAVE Datapage ID (corresponding record in the electronic case report form is missing) will be excluded from the analysis.

4.6 Blind Review

There will be two data assessment lists. The first one will occur after primary completion and the second one will occur after end of study. The results of both data lists will be documented in separate lists of important deviations, validity findings and assignment to analysis set(s). Any changes to the statistical analysis prompted by the results of the review of study data will be documented in an amendment and, if applicable, in a supplement to this SAP.

The results of the final data assessment will be documented in the final list of important deviations, validity findings and assignment to analysis sets. Pharmacodynamic values to be excluded from statistical analysis will be documented in the list of pharmacodynamic values to be flagged as invalid.

5. Analysis Sets

Final decisions regarding the assignment of subjects to analysis sets will be made during the review of study data and documented in the final list of important deviations, validity findings and assignment to analysis set(s) (see section 4.6).

The following populations are defined:

Population	Description
Enrolled	All subjects who sign the ICF
Full Analysis Set	All subjects randomly assigned to study intervention.
Safety Analysis Set	All subjects randomly assigned to study intervention and who took at least 1 dose of study intervention. Subjects will be analyzed according to the intervention they actually received.
Pharmacokinetic analysis set	All osocimab-treated subjects with at least 1 PK sample in accordance with the PK sampling schedule (Section 1.3 and Section 8.5 of the study protocol) and without deviation from the protocol that would interfere with the evaluation of the PK data will be included in the PK analysis.
Pharmacodynamic analysis set	All subjects with at least 1 PD sample in accordance with the PD sampling schedule and without deviation from the protocol that would interfere with the evaluation of the PD data will be included in the PD analysis.
Listing only set	All subjects who signed ICF but are not randomized.

In accordance with the “population” attribute of the primary estimand, the primary analysis set is the safety analysis set.

Supplementary analyses of the efficacy variables will be performed on the full analysis set.

6. Statistical Methodology

In general, the evaluations will be conducted on each osocimab group and on the placebo group.

In addition, the primary safety and efficacy variables will be analysed descriptively for the following groups:

- each osocimab group, placebo high dose group, placebo low dose group,
- pooled osocimab group, pooled placebo group.

For the primary analysis and all analyses conducted at primary completion which will occur once the last patient completed the end of main treatment phase visit, only the main treatment period will be considered. The partial data of a subject’s extended treatment period up until primary completion may be presented in separate tables.

At full study completion, also the extension treatment and follow-up period will be considered.

Incidence rates and cumulative incidences will be calculated only for endpoints with at least 3 events in at least one treatment arm. Hazard ratios (cause specific and subdistribution) will be calculated only if in addition at least 1 event in each of the compared treatment arm occur.

6.1 Population characteristics

6.1.1 Demography and baseline characteristics

Demographic and baseline data will be evaluated descriptively for the SAF as well as for the FAS, by treatment groups and overall. No statistical tests will be performed to compare these characteristics across treatment groups.

Descriptive statistics (such as mean, standard deviation, median, quartiles (inter quartile range), minimum and maximum) will be provided for continuous variables such as

- Age at Screening
- Year of birth
- Body weight
- Body height
- Calculated BMI
- Hemoglobin level
- Platelet count
- Dialysis vintage (time since start of chronic dialysis)
- aPTT

Counts and (appropriate) percentages will be provided for categorical variables such as

- Sex (male/female)
- Race (American Indian or Alaska Native, Asian, Black or African American, Multiple, Native Hawaiian or Other Pacific Islander, Not Reported, White)
- Ethnicity (Hispanic or Latino, Not Hispanic or Latino, Not Reported)
- Low dose ASA use (yes/no)
- Dialysis access via catheter (yes/no)
- Diabetes mellitus (yes/no)
- Atrial Fibrillation (AF) (yes/no)
- Prior CV events (Stroke, TIA, MI, DVT, PE) (yes/no)
- Hemodiafiltration (yes/no)

Reasons for exclusion from analysis populations will be summarized.

6.1.2 Medical history

Medical history data will be evaluated by frequency tables, showing the number and percentage of subjects with medical history findings (i.e. previous diagnoses, diseases or surgeries) that started before signing of the informed consent and that are considered relevant to the study using MedDRA Primary System Organ Class / Preferred Term.

